9.3 Variables

9.3.1 Patient characteristics and drug utilization

The following variables, including risk factors/potential confounders for the outcomes under study, will be collected for comparison between the two cohorts:

- age and sex distribution at index date; 
- dose of index drug at index date and duration of treatment (including pack size); 
- diagnosis associated with the prescribing of the index drug; 
- proportion of patients defined as naïve, non-naïve, recent switchers and distant switchers; 

- type and duration of other anticoagulant use before the index date among the non-naïve group; ✓
- number of pregnant women at index date; ✓
- number of pregnancies after the index date; ✓
- use of specific prescribed medications both in the year before the index date and following the index date, confirming the ACS indication: antiplatelet drugs (low-dose acetylsalicylic acid, clopidogrel, dipyridamole, prasugrel, ticlopidine and ticagrelor); ✓
- use of other prescribed medications both in the year before the index date and following the index date: anticoagulants (including dabigatran etexilate and apixaban), antiarrhythmic drugs, antihypertensive drugs, statins, anti-diabetic agents, non-steroidal anti-inflammatory drugs, oral steroids, acid-suppressive drugs, disease-modifying anti-rheumatic drugs, antidepressants, antipsychotic drugs, oral contraceptives, hormone-replacement therapy, strong inhibitors of either cytochrome P450 3A4 or P-glycoprotein (e.g. the systemic azole antimycotics ketoconazole, itraconazole, voriconazole and posaconazole and the HIV-protease inhibitor ritonavir), strong CYP3A4 inducers (e.g. rifampicin, phenytoin, carbamazepine or phenobarbital) and fluconazole; ✓
- renal disease based on diagnoses, most recently recorded before the index date and in following the index date, with estimated glomerular filtration rate (eGFR) or creatinine clearance (CrCl) to be obtained where available; ✓

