- comorbidity based on diagnoses most recently recorded before the index date and in following the index date, such as haemorrhagic disease, liver disease, pancreatic disease, cancer (including the presence of malignant neoplasm), cardiovascular disease, cardiovascular risk factors (hypertension, diabetes mellitus, hyperlipidaemia and obesity), peripheral arterial disease, respiratory disease (asthma and chronic obstructive pulmonary disease), rheumatoid arthritis, osteoarthritis, gastrointestinal disease (recent gastrointestinal ulceration [including peptic ulcer disease], gastritis and duodenitis, dyspepsia and gastroesophageal reflux disease), oesophageal varices, arteriovenous malformations, vascular aneurysms or major intraspinal or intracerebral vascular abnormalities, thyroid disease, surgical procedures (including PCI, CABG, and recent brain, ophthalmic or spinal surgery, where recorded), presence of a prosthetic heart valve (if recorded), alcohol-related disorders, ventricular arrhythmia, anaemia, and history of intracranial haemorrhage, urogenital bleeding and gastrointestinal bleeding; if possible, a CHADS score will be calculated based on the presence of congestive heart failure, hypertension, age, diabetes mellitus and prior stroke or transient ischaemic attack; also, where possible, a HAS-BLED score for major bleeding risk (hypertension, renal disease, liver disease, stroke history, prior major bleeding or predisposition to bleeding, age > 65, medication usage predisposing to bleeding, alcohol usage history, labile INR [if available]) will be calculated; ✓
- smoking status, body mass index (BMI) and Townsend score: most recently recorded before the index date and following the index date;
- healthcare utilization in the year prior to the index date (e.g. PCP visits, outpatient visits and hospital admissions). ✓

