9.3.2 Safety and effectiveness outcomes

For each outcome, potential cases will be identified using diagnostic Read codes ([Annex 3](#)) and, where appropriate, computerized patient profiles (including any free text comments) will be reviewed with all identifying information removed. Diagnostic confirmation using patients' original medical records will be performed where possible. When required, information contained in HES among the subset of practices linked to THIN, will be used.

For the purpose of this study, clinically relevant bleedings will be defined as bleedings leading to hospital admission or referrals to a specialist. This restriction is needed to minimize differential misclassification caused by the variability in patients' behavior in seeking care for less severe bleedings. Similarly, the physicians' attitude towards recording these events may differ between new drugs and standard of care. The consequence of restricting to bleedings identified through hospitalization or referrals is that bleedings leading to death before contact with a health care professional or hospital admission might be missed. It is assumed that the number of bleeding events missed due to this restriction is small. Nevertheless, the magnitude and impact of this restriction will be assessed in another study of this PASS program (Swedish Record-linkage study).

9.3.2.1 Occurrence of intracranial haemorrhage, gastrointestinal bleeding and urogenital bleeding: case definitions

Intracranial haemorrhage (Annex 3, Table 4)

Cases of intracranial haemorrhage will be identified in patients referred to a specialist or admitted to hospital that meet the criteria for one of the three following categories:

- incident cases of intracerebral haemorrhage recorded following or in association with computed tomography, magnetic resonance imaging (MRI) or X-ray angiography, or an appropriate therapeutic procedure.
- incident cases of subarachnoid haemorrhage recorded following computed tomography, MRI, X-ray angiography or lumbar puncture, or an appropriate therapeutic procedure.
- incident cases of epidural, dural, subdural and arachnoid haemorrhage recorded following computed tomography, MRI, X-ray angiography or lumbar puncture, or an appropriate therapeutic procedure.

Gastrointestinal bleeding (Annex 3, Table 5)

A patient will have to meet the following criteria to be considered a case of gastrointestinal bleeding:

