9.7.2.1 Primary safety outcomes

Crude incidence rates will be estimated for each of the three primary adverse outcomes in both cohorts. Age- and sex-adjusted rate ratios with 95% CIs will be estimated for each of the three primary adverse outcomes comparing rivaroxaban with standard of care using Poisson regression analysis based on person–time contribution (current, recent and past use as defined in [Section 9.7.2](#)).

Where numbers and data permit, adjustment will be made for baseline medication and comorbidity variables described in the drug utilization section, including indication and history of adverse outcomes (referral or hospitalization for haemorrhagic stroke, gastrointestinal bleeding or urogenital bleeding recorded at any time before the index date).

If numbers of final cases permit, estimation of the relative risk among rivaroxaban users will be adjusted for known risk factors of the specific outcome using logistic regression models in nested case-control analyses.

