9.7.2.4 Outcomes related to effectiveness

Crude incidence rates will be estimated for each effectiveness outcome in both cohorts. Age- and sex-adjusted rate ratios with 95% CIs will be estimated for each effectiveness outcome comparing rivaroxaban with standard of care using Poisson regression analysis. Where numbers and data permit, adjustment will be made for baseline medication and comorbidity variables described in the drug utilization section.

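### The stated adjustment set for the Poisson rate ratios leaves out smoking, BMI, Townsend score and prior-year healthcare use, although section 9.3.1 collects them in a list that includes potential confounders

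*Protocol*

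**What the plan says.** Section 9.3.1 opens by stating that its variables, "including risk factors/potential confounders for the outcomes under study, will be collected for comparison between the two cohorts". Co-medications and comorbidities have bullets of their own. Two further bullets stand apart from them: "smoking status, body mass index (BMI) and Townsend score: most recently recorded before the index date" (post-index values are collected too), and "healthcare utilization in the year prior to the index date", with primary care visits, outpatient visits and admissions as examples.

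For the primary outcomes, section 9.7.2.1 starts with a base model: "Age- and sex-adjusted rate ratios with 95% CIs will be estimated for each of the three primary adverse outcomes". If numbers and data allow, "adjustment will be made for baseline medication and comorbidity variables described in the drug utilization section, including indication and history of adverse outcomes". If there are enough cases, a nested case-control analysis follows, in which "estimation of the relative risk among rivaroxaban users will be adjusted for known risk factors of the specific outcome using logistic regression models".

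Sections 9.7.2.2 (other bleeding), 9.7.2.3 (non-infective liver disease) and 9.7.2.4 (effectiveness) repeat the age and sex base and the same conditional sentence: "adjustment will be made for baseline medication and comorbidity variables described in the drug utilization section". They do not mention indication or bleeding history, and they plan no case-control analysis.

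**The concern.** The protocol does not leave the covariate set open. It names classes of covariate, and those classes are narrower than its own list of variables that include potential confounders. Even if numbers allow the full stated adjustment, the text does not bring smoking, Townsend score, healthcare use, or BMI beyond obesity into the Poisson models.

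Healthcare use deserves most attention. A primary bleeding outcome counts only if the patient was referred or admitted, so being counted depends partly on contact with care. Section 9.3.2 recognises that patients vary "in seeking care for less severe bleedings" and restricts the outcomes to reduce the resulting misclassification. For outcomes that a referral alone can satisfy, the restriction reduces the problem without removing it. If the cohorts differ in prior contact with care, for example because recent switchers from warfarin have had INR monitoring visits, part of a rate ratio could reflect detection and referral rather than the drug. The bias could go in either direction.

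**Working it through.** **1. Variables collected against variables named for adjustment**

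| Variable in 9.3.1 | Poisson models, primary (9.7.2.1) | Poisson models, other outcomes (9.7.2.2 to 9.7.2.4) | Nested case-control (primary only, conditional) |
|---|---|---|---|
| Age, sex | named | named | not stated |
| Co-medication, comorbidity (including obesity) | named, conditional | named, conditional | where a risk factor |
| Indication, bleeding history | named, conditional | not named as such | where a risk factor |
| Smoking | not named | not named | may enter |
| BMI | only through obesity | only through obesity | may enter |
| Townsend score | not named | not named | unclear |
| Prior-year healthcare use | not named | not named | unclear |

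The narrowing can be seen within the protocol. Section 9.7.1 applies its descriptive odds ratios to the 9.3.1 variables as a whole, while the outcome sections refer to two classes of them. The ENCePP checklist (item 7.1) answers that known confounders are addressed and points to pages 12 and 13, about where the contents list places 9.3.1.

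**2. Where care-seeking could act (case definitions in 9.3.2)**

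- Gastrointestinal and urogenital bleeding: referral is enough. The urogenital codes in Annex 3 include microscopic haematuria and intermenstrual bleeding, which plausibly come to light through consultation.
- Non-infective liver disease: referral is enough, and raised laboratory values are required, so a test must have been done.
- Intracranial haemorrhage: referral or admission, together with imaging, lumbar puncture (for some types) or a therapeutic procedure. Much less exposed.
- Other bleeding, DVT/PE, ischaemic stroke, MI: admission required. Less exposed. Smoking, body weight and deprivation may still matter here.

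**3. The protocol's own study size (section 9.5)**

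Inputs: 5 per 1000 person-years; 12,000 and 48,000 patient-years; exclude a 50% increase; 80% power. Alpha is not stated; I assume two-sided 0.05.

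- Expected events at equal rates: 0.005 × 12,000 = 60 and 0.005 × 48,000 = 240.
- Events required: (1.96 + 0.842)² / (0.2 × 0.8 × (ln 1.5)²) = 298.4, so 299. That is 299 × 0.2 / 0.005 = 11,960 rivaroxaban patient-years, against 12,000 stated.
- SE of the log rate ratio: √(1/60 + 1/240) = 0.1443. Power: Φ(ln 1.5 / 0.1443 − 1.96) = 80.2%. The stated figure reproduces.

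**4. Illustration of a left-out marker (all inputs assumed)**

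Let a binary marker of high prior healthcare use multiply the rate of recorded events by R, with prevalence p1 in the rivaroxaban cohort and p0 in the comparator. The bias factor is B = (1 + p1(R − 1)) / (1 + p0(R − 1)).

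Power to exclude 1.5 when the true ratio is 1 is Φ(ln(1.5/B) / 0.1443 − 1.96). With the imbalance reversed, the ratio is multiplied by 1/B, and the chance of wrongly excluding a true 1.5 is Φ(ln B / 0.1443 − 1.96).

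| R | p1 v p0 | B | Power to exclude 1.5 | 1/B (reversed) | False exclusion of a true 1.5 |
|---|---|---|---|---|---|
| any | equal | 1 | 80.2% | 1 | 2.5% |
| 1.5 | 40% v 30% | 1.20/1.15 = 1.043 | 71.0% | 0.958 | 4.8% |
| 1.5 | 50% v 30% | 1.25/1.15 = 1.087 | 60.7% | 0.920 | 8.3% |
| 2 | 40% v 30% | 1.4/1.3 = 1.077 | 63.1% | 0.929 | 7.4% |
| 2 | 50% v 30% | 1.5/1.3 = 1.154 | 44.3% | 0.867 | 16.6% |

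The last column keeps the SE at 0.1443. At a true ratio of 1.5 the rivaroxaban cohort would have 60 × 1.5 = 90 events and the SE would be √(1/90 + 1/240) = 0.1236. The R = 2 rows then become 8.7% and 21.1%.

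**The case against.** The best defence is that not naming a variable does not exclude it. Section 9.6 has several multivariable models fitted before the final one is chosen. Section 9.7.2.6 provides a missing-value category for potential confounders in general, a rule that suits smoking and BMI well. Section 9.7.2.7 says the descriptive part may reveal unexpected biases that can then be allowed for. Section 9.3.1 says only that its list includes confounders, not that every entry is one. An itemised covariate list may also stand in an analysis plan that is not at hand.

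Much of this stands as a limit on the point. A reader might infer that the protocol adjusts only for medication and comorbidity, or that these four variables are kept out of every estimate. The text does not support either reading. Age and sex are always in the model. Indication and bleeding history are named for the primary outcomes. Obesity is a listed comorbidity. The nested case-control estimate is open to known risk factors. Nor does the protocol ignore care-seeking, since restricting outcomes to referral or admission is its stated remedy.

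The defence does not close the gap. Section 9.6 permits the variables without committing to any. Section 9.7.2.6 governs missing values, not selection. Section 9.7.2.7 concerns biases that are unexpected, whereas these variables were anticipated and collected. The case-control analysis is conditional, stops at the primary outcomes, and does not clearly reach deprivation or healthcare use. An unseen analysis plan could widen the set, but the protocol sentence it would start from names the narrower one.

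The illustration has weak footing and should be read that way. Its event counts come from haemorrhagic stroke, which is little exposed to care-seeking. The assumed imbalance would also have to remain after adjustment for medication, comorbidity and bleeding history, which overlap with healthcare use.

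**Conclusion.** The point holds as a gap in the stated adjustment set of the Poisson rate ratios, for the primary, secondary safety and effectiveness outcomes alike. It is worth correcting because the baseline data are already collected. It is not an error of fact, and the documents do not show that any estimate will be biased.

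Residual confounding by care-seeking is most plausible for gastrointestinal bleeding, urogenital bleeding and liver disease, and less so where admission or imaging is required. Its size cannot be derived from the protocol. Under the assumed inputs, the rate ratio moves by a factor of 1.04 to 1.15 in one direction or 0.96 to 0.87 in the other. The loss of power and the false-exclusion figures depend wholly on those assumptions and on event counts planned for a different outcome. They show what a moderate imbalance could do, not what is expected.

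**What to change.** In sections 9.7.2.1 to 9.7.2.4, extend the adjustment sentence to smoking status, BMI, Townsend score and healthcare utilization in the year before index (primary care visits, outpatient visits and admissions, in categories), under the condition on numbers and data that already governs the other covariates. Specify that only values recorded before the index date are used, because 9.3.1 also collects later values of smoking, BMI and Townsend score, and these may be affected by treatment or outcome. Handle missing values with the separate category of section 9.7.2.6. If any of the four is left out on purpose, give the reason.

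The cost is one sentence in each of four sections and a few more parameters per model, including missing-value categories where needed. No new data are required. For outcomes with few events, the existing condition already allows a smaller model.

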9.7.2.2 Secondary safety outcome: other bleeding

Crude incidence rate will be estimated for “other bleeding” in both cohorts. Age- and sex-adjusted rate ratios with 95% CIs will be estimated comparing rivaroxaban with standard of care using Poisson regression analysis. Where numbers and data permit, adjustment will be made for baseline medication and comorbidity variables described in the drug utilization section.

9.7.2.3 Secondary safety outcome: non-infective liver disease

Crude incidence rate will be estimated for non-infective liver disease in both cohorts. Age- and sex-adjusted rate ratios with 95% CIs will be estimated for non-infective liver disease comparing rivaroxaban with standard of care using Poisson regression analysis. Where numbers and data permit, adjustment will be made for baseline medication and comorbidity variables described in the drug utilization section.

9.7.2.4 Outcomes related to effectiveness

Crude incidence rates will be estimated for each effectiveness outcome in both cohorts. Age- and sex-adjusted rate ratios with 95% CIs will be estimated for each effectiveness outcome comparing rivaroxaban with standard of care using Poisson regression analysis. Where numbers and data permit, adjustment will be made for baseline medication and comorbidity variables described in the drug utilization section.

9.7.2.5 Sub-analysis by renal status

Results from laboratory tests performed in primary care are automatically recorded in THIN.

- As in previous studies we will use serum creatinine values to compute estimated glomerular filtration rate (eGFR). We will calculate the eGFR using the Modification on Diet in Renal Disease (MDMR) formula: $eGFR = 186(\text{Serum Creatinine}^{-1.154} \times \text{age}^{-0.203}) \times 0.742$ [if female].
- In THIN, creatinine values are recorded using International System of Units (SI) as $\mu\text{mol/L}$, and we will divide serum creatinine value by a factor of 88.4 to convert it to conventional unit as mg/dL . Additional clinical information on dialysis and kidney transplantation will also be ascertained.

The subset of patients with recorded renal status will be analysed to determine:

- the proportion of patients with normal renal function ($\text{CrCl} > 80 \text{ mL/min}$); mild ($\text{CrCl} < 80\text{--}50 \text{ mL/min}$), moderate ($\text{CrCl} < 50\text{--}30 \text{ mL/min}$) or severe ($\text{CrCl} < 30\text{--}15 \text{ mL/min}$) renal impairment; and the proportion with end-stage renal disease ($\text{CrCl} < 15 \text{ mL/min}$) or a requirement for dialysis;
- initial indication for rivaroxaban;
- rivaroxaban dose received;
- crude incidences (calculated as described above) of primary safety outcomes and outcomes related to effectiveness by renal function and by dose.

It is likely that a potential misclassification of renal failure will be more pronounced in mild renal failure whereas severe forms of renal failure most likely will be readily identified.

9.7.2.6 Strategy for handling missing data

As a general strategy, no data imputation strategies will be applied to supplement missing data. The requirement for inclusion is complete data for critical variables such as exposure to rivaroxaban or standard of care and hospitalizations for bleedings or any other outcome event; otherwise this individual is not eligible to be a member of the study population. However, missing values may occur in a small proportion for potential confounder or effect modifying variables. In this case, individuals with missing values will be kept in the analysis and a separate category will be created for missing values of that variable. In sub-analyses to evaluate confounding or effect modification by variables with a large proportion of missing values (if any), the evaluation will be considered to be conducted on the subset with complete data for the variable of interest.

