9.1 Study design

This study has a cohort design including nested case–control analyses.

Cohorts of first-time users of either rivaroxaban or comparators will be identified using the date of first prescription (index date) of the respective drug (index drug) (Figure 1).

A patient will be considered eligible to enter the study cohort as a first-time user of rivaroxaban or a first-time user of “standard of care” when he or she has a first prescription of the drug recorded during the enrolment period. In the UK, for VTE prevention, DVT/PE treatment and SPAF, standard of care is treatment with the most widely used vitamin K antagonist, warfarin, and for the secondary prevention of ACS, standard of care is antiplatelet drug(s) such as low-dose acetylsalicylic acid, clopidogrel, dipyridamole, prasugrel, ticlopidine and ticagrelor.

Patients who have any record of being prescribed their index drug prior to the enrolment period or who qualify as members of both cohorts on the same day, will be excluded. If a patient qualifies as first-time user of both rivaroxaban and “standard of care” comparison drug during the enrolment period, she/he will be assigned to the cohort of drug first prescribed during the enrolment period, with the date of this prescription being the index date.

Many patients with ACS have a history of ischaemic heart disease for which platelet inhibition is standard treatment, and thus exclusion of patients with prior use of platelet inhibitors risks excluding a majority of typical ACS patients. Therefore, those who have been using one or more platelet inhibitors will remain eligible to enter the study.

Standard of care for ACS patients is combination therapy, and as such cohort assignment will be based on first use of rivaroxaban (in combination with aspirin or clopidogrel, or multi-antiplatelet therapy), or use of aspirin and clopidogrel and/or other antiplatelet medications.

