9.2 Setting

All patients aged 2 years and above who have been enrolled with a primary care physician for at least 1 year and had their first prescription recorded in the database at least 1 year ago will be included.

The population included in THIN is representative of the UK as a whole in terms of age, sex and geographic distribution ([Bourke, Dattani et al. 2004](#); [Blak, Thompson et al. 2011](#)). THIN has been extensively validated for use in pharmacoepidemiology ([Lewis, Schinnar et al. 2007](#)), and has been used successfully in studies of bleeding risk ([Tata, Fortun et al. 2005](#); [Smeeth, Cook et al. 2006](#); [García Rodríguez and Barreales Tolosa 2007](#); [de Abajo and Garcia-Rodriguez 2008](#); [Massó González and García Rodríguez 2008](#); [Raine, Wong et al. 2009](#); [Cea Soriano and García Rodríguez 2010](#); [Gaist, Wallander et al. 2013](#); [Garcia-Rodriguez, Gaist et al. 2013](#)).

The enrolment period will start on the day after rivaroxaban receives first marketing authorization for the ‘treatment of DVT and long-term secondary prevention of recurrent DVT and PE’. End of enrolment will be 31 December 2017 and end of follow-up will be 31 December 2018. Interim reports will be provided for data collected 2 and 4 years after the date that rivaroxaban receives NICE approval for DVT treatment (see [Section 6](#) for detailed milestones).

To study outcomes of interest ([Section 8](#)) for patients receiving rivaroxaban and comparators for DVT/PE treatment, SPAF or ACS, the same source population will be used as in the drug utilization study.

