9.7.2 Safety and effectiveness outcomes

The two cohorts (of first-time users of rivaroxaban and first-time users of comparators) will be followed up from the index date until 12 months after the end of the enrolment period for potential outcomes (safety and effectiveness). For each outcome, the first referral or hospitalization for that

outcome during the follow-up period will be identified. A separate follow-up will be performed for each of the outcomes.

Crude incidence rates will be estimated in both cohorts for DVT/PE treatment, SPAF and ACS. Incidence will be computed using the person–time contribution of the study cohorts, stratified into current, recent, past and non-use. Current use will refer to person–time up to 7 days after the end of supply of the index drug, recent use will refer to person–time up to 90 days after the end of current use, past use will include all person–time contribution after the end of recent use up to 1 year after the end of current use, non-use will include all remaining time person–time contribution after past-use until end of follow-up.

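### Section 9.7.2.6 makes complete outcome data a condition of cohort membership, which conflicts with the protocol's own eligibility rules; its missing-value category for confounders leaves residual confounding unless missingness is small

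*Protocol*

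**What the plan says.** Section 9.7.2.6 fixes three rules.

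- **Inclusion.** "The requirement for inclusion is complete data for critical variables such as exposure to rivaroxaban or standard of care and hospitalizations for bleedings", extended in the same sentence to any other outcome event. The stated consequence of incomplete data is: "otherwise this individual is not eligible to be a member of the study population".
- **Imputation.** As a general strategy, "no data imputation strategies will be applied to supplement missing data".
- **Confounders and effect modifiers.** Missing values are expected in a small proportion, with no figure given. For these, "individuals with missing values will be kept in the analysis and a separate category will be created for missing values of that variable". Where a variable has a large proportion missing, sub-analyses of confounding or effect modification are to be considered in the subset with complete data.

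Elsewhere, eligibility rests on what is known at the index date. Section 9.1 uses the first prescription issued within the enrolment window: "A patient will be considered eligible to enter the study cohort as a first-time user of rivaroxaban or a first-time user of" (the comparator is named next). Section 9.2 adds age and registration: "All patients aged 2 years and above who have been enrolled with a primary care physician for at least 1 year", with a first recorded prescription at least a year earlier. Neither mentions outcome data. Under Section 9.7.2 the cohorts "will be followed up from the index date until 12 months after the end of the enrolment period for potential outcomes".

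**The concern.** Whether a patient's outcome data are complete can be known only after the index date. A membership rule that uses it lets later information decide who was ever in the cohort. In a study whose main products are crude incidence rates and rate ratios for bleeding, that can lower the rates. It can also distort the ratio if the people removed differ in outcome and in number between rivaroxaban and standard of care.

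The confounder rule raises a different problem. In a non-randomised comparison, patients placed in a missing category are compared across cohorts without adjustment for the missing variable. Their part of the estimate stays confounded even if values are missing completely at random, so the adjusted ratio moves back towards the crude one.

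**Working it through.** **1. The inclusion clause against the rest of the protocol.**

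| Section | Basis for membership | When known |
|---|---|---|
| 9.1 | First prescription of the index drug, no earlier use of it, not in both cohorts on one day | Index date |
| 9.2 | Age, registration, prescription history | Index date |
| 9.7.2.6 | Complete exposure and outcome data | After the index date |

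The third row conflicts with the first two. Sections 9.7.2 and 9.7.2.1 analyse person-time by Poisson regression, so a record that ends early can contribute until it ends. The analysis does not need the condition.

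**2. What the clause could do.** Section 9.7.2.6 gives no figure of its own. The study size in Section 9.5 gives a scale: 5 per 1000 person-years, 12,000 and 48,000 person-years, so 60 + 240 = 300 expected events if the rate ratio is 1. It reproduces at two-sided alpha 0.05 (assumed, as the protocol states no alpha):

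- Events needed = (1.960 + 0.842)² / (0.2 × 0.8 × (ln 1.5)²) = 298.4, rounded up to 299.
- With 300 events, SE(log RR) = √(1/60 + 1/240) = 0.144 and the power to exclude 1.5 is 80.2%.

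Suppose the clause removed a fraction a of event-bearing rivaroxaban patients and b of event-bearing comparator patients. Events are rare, so total person-time barely changes and RR ≈ (1 − a)/(1 − b). The fractions are assumptions chosen only to show behaviour:

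| a | b | RR (truth 1) | Power to exclude 1.5 |
|---|---|---|---|
| 0 | 0 | 1.00 | 80% |
| 10% | 10% | 0.90/0.90 = 1.00 | 76% |
| 10% | 20% | 0.90/0.80 = 1.125 | 46% |
| 20% | 10% | 0.80/0.90 = 0.889 | 91% |

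Equal removal leaves the ratio alone but understates both rates by about 10%. Unequal removal moves the ratio in either direction, and the last row would be falsely reassuring. The protocol supplies neither a nor b, and both could be close to zero.

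**3. The missing category.** Assumed inputs: binary confounder with prevalence 0.30 in the comparator cohort, odds ratio 3 with exposure, rate ratio 3 with the outcome, true drug rate ratio 1, values missing completely at random.

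- Rivaroxaban prevalence: odds = 3 × 0.30/0.70 = 1.286, so p = 1.286/2.286 = 0.5625.
- Crude RR = (1 + 2 × 0.5625)/(1 + 2 × 0.30) = 2.125/1.600 = 1.33.
- Within the missing stratum the ratio is also 1.33; within each observed stratum it is 1.

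Mantel-Haenszel pooling over absent, present and missing, with 20% of person-time on rivaroxaban (the 1:4 split of Section 9.5) and 10% missing:

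- Numerator terms: 0.0681 + 0.2068 + 0.0340 = 0.3089.
- Denominator terms: 0.0681 + 0.2068 + 0.0256 = 0.3005.
- RR = 0.3089/0.3005 = 1.028.

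| Missing | RR, 20% exposed | RR, 50% exposed |
|---|---|---|
| 5% | 1.014 | 1.015 |
| 10% | 1.028 | 1.031 |
| 20% | 1.057 | 1.062 |
| 30% | 1.087 | 1.094 |
| 50% | 1.150 | 1.159 |

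A weaker confounder (rate ratio 2 with the outcome, prevalence 20% against 30%) gives 0.992 at 10% missing and 0.976 at 30%. If the confounder is commoner among comparator patients, the bias is downward.

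**4. Is missingness small?** The protocol gives no percentage. Section 9.3.1 obtains eGFR or creatinine clearance only where available, Section 9.7.2.5 analyses only patients with recorded renal status, and Section 9.9 names alcohol intake as poorly recorded. These passages make the premise uncertain for some variables; they do not refute it.

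**The case against.** A reader might infer that patients who die, leave the practice or have an unconfirmed event are dropped from the cohort. The protocol does not say so, and other sections point the other way. All-cause mortality is an objective (Section 8.2) with its own ascertainment (Section 9.3.2.4). Confirmation from original records is done only where possible (Sections 9.3.2 and 9.8), and nothing makes its absence a ground for exclusion. Person-time rates accommodate early departure. In a record database the absence of a code normally counts as no event, so the clause may have almost no effect. All of this stands, and for that reason no size can be put on the selection. It does not rescue the wording: either the clause does nothing, or it does something the analysis should not do. Detailed censoring rules may properly sit in a statistical analysis plan, and their absence here is not part of this point.

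On confounders, the category is tied to small missingness, and complete-data evaluation is foreseen for variables with much missing data. The cohort adjustment in Sections 9.7.2.1 to 9.7.2.4 names baseline medication and comorbidity variables, where no code is usually read as no; smoking and BMI are listed separately in Section 9.3.1. This also largely stands, and it confines the problem to variables that are truly incomplete. What remains is that the complete-data provision covers only sub-analyses, and that no figure separates a small from a large proportion.

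**Conclusion.** The point holds in two limited parts.

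- **Inclusion clause.** Wrong as written, because it uses post-index information and contradicts Sections 9.1 and 9.2. Its practical effect is undetermined, from nil to a real distortion. Understated rates require event-bearing patients to be excluded disproportionately. A biased ratio also requires that exclusion to differ by cohort. Neither is shown by the document, so selection bias is a possibility to close off and not an established fact.
- **Missing category.** Residual confounding follows in principle. Under the strong confounder assumed above it is about 1% to 3% of the rate ratio at 5% to 10% missing, about 6% at 20%, 9% at 30% and 15% to 16% at 50%. Within the small proportion that the protocol assumes, it is minor. It becomes material only if an important confounder is often unrecorded, which the protocol neither quantifies nor rules out. Confounder strength, prevalence and missingness are assumptions, not values from the document.

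The correction should be made because it is specific and cheap. Neither part invalidates the study.

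**What to change.** 1. Delete the outcome part of the inclusion sentence in Section 9.7.2.6. Decide eligibility on data up to the index date, in line with Sections 9.1 and 9.2, and let patients with incomplete follow-up contribute person-time until their record ends.
2. Report the proportion missing for each baseline confounder, by cohort.
3. For the adjusted rate ratios, use multiple imputation of incompletely recorded baseline confounders, with exposure, outcome and person-time in the imputation model. Keep the missing-category and complete-data results as sensitivity analyses.

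The cost is a wording change and modest programming; no new data are needed. The drawback is that multiple imputation assumes values are missing at random given the variables in the model. The sensitivity analyses probe that assumption but cannot prove it.
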